1.0 Objectives

1.1 Study Objectives

We hypothesize that ruxolitinib 1.5% cream is an effective therapy for **Hidradenitis Suppurativa** patients through inhibition of inflammatory activity.

We aim to:

- Demonstrate the clinical efficacy of ruxolitinib 1.5% cream in decreasing the clinical disease activity after 16 weeks of treatment.
- Investigate the impact of ruxolitinib 1.5% cream on skin inflammation through translational analyses of skin biopsy samples.

1.2 Primary Study Endpoints

The primary efficacy measure is the proportion of participants that achieve HiSCR (is the total number of abscess and inflammatory count of the participants lesions) at Week 16 with topical ruxolitinib 1.5% cream as compared to Baseline (Week 0). The HiSCR is defined as at least a 50% reduction in the total abscess and inflammatory nodule count (AN count) for all study body sites with no increase in abscess count and no increase in draining fistula count relative to Baseline. The primary efficacy analysis will be carried out on all participants who complete 16 weeks of treatment.

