3.3 Early Withdrawal of Subjects

3.3.1 Criteria for removal from study

Some possible reasons for an early withdraw might be subjects require or receive treatment that is not allowed in this study, subject becomes pregnant, subject experiences side effects from the study treatments that they find unacceptable, HS worsens according to the study doctor's assessment, or subject does not follow instructions.

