In the event of an acutely painful lesion that requires immediate intervention, the investigator and participant will have the option to perform protocol-allowed interventions. Two types of interventions are permitted: injection with intralesional triamcinolone acetonide suspension (up to 40 mg in total at the same visit) and/or incision and drainage. New systemic and topical therapies following incision and drainage, including antibiotics, are prohibited. Participants should continue using the topical study therapy. From Day 1 through Week 16, an intervention can occur on a maximum of 2 different lesions at the same visit or on the same lesion at 2 different study visits. The same lesion cannot be treated 2 times during the same visit. If participants require more than 3 interventions before Week 16, then the study drug will be discontinued for those participants. Study procedures must be performed before any interventions. Any lesion undergoing an intervention will be documented in the lesion count worksheet.

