8.0 Subject Numbers and Statistical Plan

8.1 Number of Subjects

We aim to enroll at least 18 subjects to complete the interventional study to assess the primary endpoint. Anticipating screen failures and loss-to-follow-up we anticipate screening and enrolling approximately 24 people with hidradenitis suppurativa. No additional participants with *any* biologic use will be enrolled after 30% of participants with stable dosage and frequency of a biologic are enrolled.

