8.2 Sample size determination

Based on the placebo and effect responses for adalimumab in the PIONEER trials (Kimball, 2016) for moderate-to-severe HS, the HiSCR response rate in the placebo group was approximately 27% (26.0% and 27.6%) and HiSCR rates of 42-59% for adalimumab. In mild-to-moderate and moderate-only HS treated with apremilast, the placebo HiSCR rate was 0% and in the response rate in the intervention groups was 53-55% (Kerdel 2019, Vossen 2019).

With a sample size of at least 18 participants, we will have sufficient power to determine if the HiSCR response rate for topical ruxolitinib 1.5% cream is 55% and significantly different from a 20% (or lower) placebo response rate with a power of 80% and risk of type I error of 5%. Typically, in a Simon's two-stage design, 11 patients would be accrued in the first stage and 7 additional in the second phase; however, we will accrue all in one cohort of at least 18 completed participants. The null hypothesis will be rejected if 5 or more responses are observed in 18 completed participants.

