8.3 Statistical methods

The PI cannot be involved in the primary data analysis, but can maintain involvement in the data interpretation required for authorship. The primary statistical analysis to evaluate the null hypothesis that the proportion of participants that achieve HiSCR at Week 16. P-values ≤ 0.05 will be considered significant. The primary efficacy analysis will be carried out in the ITT Population, defined as all patients who complete the study. Last-observation-carried-forward will be used for missing data.

Secondary endpoints include the mean change in the AN count at Week 16; mean change in DLQI score from Baseline to Week 16; mean change in the novel clinician-reported outcome measure (HASI, investigator-supplied) score from Baseline to Week 16; mean change in novel HS patient-reported outcome measure (HiSQOL, Investigator-supplied) from Baseline to Week 16. Secondary efficacy variables will be summarized in the ITT Population. Statistical tests from laboratory assays will be done with the assistance of Penn State biostatisticians. Analyses can include paired t-tests, repeated measure ANOVA and regression-based analyses depending on the number of replicates, samples and repeated measures captured during each assay.

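### The primary HiSCR analysis counts completers only, so likely treatment failures can leave the denominator of an uncontrolled response rate and can bias it upward

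*Combined protocol and SAP*

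**What the plan says.** Three sections tie the primary analysis to completion.

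- Section 1.2: "The primary efficacy analysis will be carried out on all participants who complete 16 weeks of treatment".
- Section 8.3: "The primary efficacy analysis will be carried out in the ITT Population, defined as all patients who complete the study". The next sentence adds: "Last-observation-carried-forward will be used for missing data".
- Section 8.2: "we will accrue all in one cohort of at least 18 completed participants", and then "The null hypothesis will be rejected if 5 or more responses are observed in 18 completed participants".

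Two exits are linked to poor efficacy. Section 3.3.1 gives as a possible reason for removal that "HS worsens according to the study" doctor's assessment. Section 7.4.6.5 says: "If participants require more than 3 interventions before Week 16, then the study drug will be discontinued for those participants".

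Section 3.3.2 asks for an early-termination assessment where one can be obtained, and Section 7.2.5 describes a combined Week 16 and early-termination visit. Neither section places these participants in the primary analysis. On numbers, Section 8.1 says: "Anticipating screen failures and loss-to-follow-up we anticipate screening and enrolling approximately 24 people with hidradenitis suppurativa".

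**The concern.** The trial has one arm. Its result is a single proportion set against 20%, so no comparator shares any selection in the denominator. Participants removed for worsening disease or stopped after repeated rescue are likely HiSCR failures. If they are left out while the trial counts up to 18 completers, the observed rate can exceed the rate among everyone treated. The chance of declaring success for a cream that does no better than 20% then rises.

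The two definitions also disagree. A participant who is off drug but attends Week 16 is excluded by Section 1.2 (16 weeks of treatment) and included by Section 8.3 (completes the study). The denominator is therefore not uniquely fixed, and the ITT label suggests a protection that the definition does not give.

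**Working it through.** **Who is in the primary set**

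| Participant | Section 1.2 | Section 8.3 | Scored as non-responder? |
|---|---|---|---|
| Withdrawn for worsening HS | out | out | no rule |
| Stopped under the rescue rule, attends Week 16 | out | in | no rule; observed count used |
| Stopped for an adverse event (18.2), attends Week 16 | out | in | no rule; observed count used |
| Leaves early, early-termination count only | out | out | no rule |

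Carrying observations forward can only fill gaps for people already in the set, so it does not bring back the first or last row.

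**Inputs.** Null rate 20%, alternative 55%, type I error 5%, power 80% and n = 18 completers come from Section 8.2. The ceiling of about 24 people comes from Section 8.1. The number who stop, L, is an assumption. Sidedness is not stated; I take one-sided 5%.

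**The plan's own figure.** For X ~ Binomial(18, p), the stated rule of 5 or more gives P(X ≥ 5 | 0.20) = 28.4% and P(X ≥ 5 | 0.55) = 99.5%. The stated 5% and 80% are not reproduced. That is a separate error. To keep it out of this point I use the smallest valid cut-off: P(X ≥ 7 | 0.20) = 5.13%, too large; P(X ≥ 8 | 0.20) = 1.63%, valid, with power 87.2% at 55%.

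**Effect of excluding those who stop.** Let the all-treated rate be 20%, with 18 completers and L who stop and would respond at rate s. The completer rate is

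p = (0.20 × (18 + L) − s × L) / 18,

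and the false-positive probability is P(X ≥ 8 | 18, p).

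| L | s = 0: p, false positive | s = 10%: p, false positive | s = 20%: p, false positive |
|---|---|---|---|
| 2 | 22.2%, 3.0% | 21.1%, 2.2% | 20%, 1.6% |
| 4 | 24.4%, 5.1% | 22.2%, 3.0% | 20%, 1.6% |
| 6 | 26.7%, 8.0% | 23.3%, 3.9% | 20%, 1.6% |

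Example, L = 4 and s = 0: p = 0.20 × 22 / 18 = 24.4%.

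Alternatively, fix the number treated at T = 18 + L, with all L who stop being non-responders. The false-positive probability is then P(X ≥ 8 | T, 0.20): 3.2%, 5.6% and 8.9% for T = 20, 22 and 24.

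**Cut-offs if everyone treated is analysed.** The smallest r with P(X ≥ r | n, 0.20) ≤ 5% is 8 for n = 18 to 21 (1.6% to 4.3%) and 9 for n = 22 to 24 (2.0% to 3.6%).

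**Power under the fix.** If m participants are scored as failures and the other n − m respond at 55%, power is P(Y ≥ r) with Y ~ Binomial(n − m, 0.55).

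| n analysed | r | m | Power |
|---|---|---|---|
| 20 | 8 | 2 | 87.2% |
| 22 | 9 | 4 | 74.7% |
| 24 | 9 | 0 | 97.3% |
| 24 | 9 | 4 | 86.9% |
| 24 | 9 | 6 | 74.7% |

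If 55% is instead the rate among everyone treated, power is 94.2%, 93.8% and 97.3% for n = 20, 22 and 24.

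**The case against.** **The efficacy exits may be rare.** Section 3.3.1 lists worsening only as a possible reason, the rescue rule needs at least four interventions, and only Weeks 4 and 8 are scheduled between Baseline and Week 16. This stands as a limit on size. It does not supply a scoring rule for those who do leave.

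**Carrying forward may have been meant for dropouts.** Pairing an ITT label with last-observation-carried-forward and an early-termination visit suggests that withdrawn participants were to be included. That intent is plausible, but Sections 1.2 and 8.2 say completers without qualification and Section 8.3 defines its own set the same way. Even on the generous reading, the set definition needs correcting.

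**The bias need not be upward.** A reader might infer that the completer rate is bound to overstate efficacy. The documents do not support that. Section 18.2 stops drug even for Grade 1 or 2 events that could be related to it, which does not require treatment failure and may remove responders. The upward direction is expected for the worsening and rescue routes; the net direction over all exits is not established.

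**Not every stop is a failure.** For the same reason, a reader might conclude that every adverse-event stop should be a primary failure. Overriding an observed Week 16 response in that way is a debatable choice of estimand, and the problem described here does not require it.

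**Conclusion.** The point holds as a possible upward bias. The completer restriction, the mismatch between Sections 1.2 and 8.3, the wrong ITT label and the missing non-responder rule are all plain in the text. The size rests on assumed stop counts, an all-treated rate of 20% and a corrected 8-of-18 cut-off. On those terms the false-positive probability passes 5% only with about four or more excluded participants who are all non-responders. With those who stop responding at 10%, it stays at 3.9% even with six. Six is an upper bound under planned enrolment, because the 24 in Section 8.1 also covers screen failures.

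A reader might also infer that this restriction explains the 28.4% error of the 5-of-18 rule. It does not: that error is present with no dropout at all. The restriction should be corrected before analysis, but its effect may be small.

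**What to change.** Use one definition in Sections 1.2 and 8.3, for example:

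*The primary efficacy set is all participants who receive study drug. Withdrawal for worsening HS (3.3.1), stopping study drug under the rescue rule (7.4.6.5), or having no Week 16 lesion count is HiSCR non-response. An early-termination count is not a Week 16 count. A participant stopped for an adverse event (18.2) stays in the set and is scored on the Week 16 count if one was observed, otherwise as a non-responder. A sensitivity analysis uses the early-termination count for these participants where one was recorded. Observations are not carried forward for HiSCR.*

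Drop the ITT label for completers and report the completer result as supportive. In Section 8.2, apply the test to the number analysed with an exact binomial cut-off against 20%, and state the sidedness.

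Cost: the primary analysis needs wording changes only, with no new visits. Participants stopped for adverse events should be asked to attend Week 16. The sensitivity analysis depends on early-termination counts, which Section 3.3.2 only undertakes to attempt. The observed rate will fall, and power can drop below the planned 80% if many stop, as in the 74.7% cases above. Treating a full 24 to protect power may mean screening more than 24.

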1.3 Secondary Study Endpoints

- Mean difference in the International Hidradenitis Suppurativa Severity Scoring System (IHS4) score from Baseline to Week 16.
- Proportion of patients who are clear or mild by IHS4 after 16 weeks of treatment.
- Mean difference in the novel clinician-reported outcome measure (HASI, investigator-supplied) score from Baseline to Week 16.
- Mean change in the Hidradenitis Suppurativa Quality Of Life (HiSQOL) instrument for 16 weeks of treatment.
- Mean change in Numerical Rating Scale (NRS) for pain (7-day) after 16 weeks of treatment.
- Proportion of participants with a 30% and at least 2-point reduction in NRS for pain (7-day) after 16 weeks of treatment.
- Mean change in Numerical Rating Scale (NRS) for pain (24-hour) after 16 weeks of treatment.
- Proportion of participants with a 30% and at least 2-point reduction in NRS for pain (24-hour) after 16 weeks of treatment.

2.0 Background

2.1 Scientific Background and Gaps

Hidradenitis suppurativa (HS) is a chronic, inflammatory skin disease of unknown etiology that causes painful swollen nodules, draining abscesses, and disfiguring scars of the skin folds that make walking, sitting, and working difficult or impossible. Malodorous drainage is humiliating and uncomfortable. HS is a devastating inflammatory condition that affects approximately 1% of adults of European descent,

similar in incidence to psoriasis, and is associated with serious comorbidities such as metabolic syndrome and diabetes.

Adalimumab, a monoclonal antibody against TNF α , is the only FDA-approved therapy and is only partially effective for 50-60% of patients. Importantly, there is only one topical medication, clindamycin, which is routinely used for the therapy of HS. This is a critical gap in the treatment of HS – there is a need for more and effective topical therapies.

Janus kinase (JAK) kinases are intracellular, non-receptor tyrosine kinases that bind to cytokine-specific receptors and, therefore, influence various aspects of the immune response. JAK1 is associated with the receptors for IFN, IL-6, and IL-10. JAK2 is mainly involved in the reaction with hematopoietic receptors as well as those for IL-12 and IL-23. JAK2 are connected with the receptors for IFN, IL-12, and IL-23. There are no published studies documenting JAK-STAT expression in HS; however, other work has shown the important role of all four kinases in other skin conditions. Importantly, IL-6 and Interferon-gamma have been shown to be elevated in HS. Topical ruxolitinib 1.5% cream, the interventional treatment in this protocol, is not available outside of a clinical study.

Some tools to measure hidradenitis suppurativa are given by administering questionnaires that specifically define how participants are feeling and how their disease affects their daily living. This includes assessing the pain level of the lesions. These are in addition to questionnaires that are obtained during clinical visits. These tools can also help to determine whether or not the assigned medication is helping the disease. The pain associated with the disease if lessened could help improve their quality of life. It is important to capture these measures prior to medication dosing. An improved quality of life could be due to the decreased amount of lesions. Additionally, clinician- reported outcomes, including counts of lesions and the HASI (scores the severity of the participants lesions) will be used to evaluate objective changes in the disease burden. The questionnaires, HiSQOL, pain scale, lesion counts and HASI will capture this for the participant.

2.2 Previous Data

The JAK family of kinases includes JAK1, JAK2, JAK3, and TYK2. The JAK-STAT (Signal Transducer and Activator of Transcription proteins (*STATs*) pathway is used by cytokines including ILs, interferons, and other molecules to transmit signals from the cell membrane to the nucleus. Upon engagement of extracellular ligands, intracellular JAK proteins, which associate with type I/II cytokine receptors, become activated and phosphorylate STAT proteins, which dimerize and then translocate into the nucleus to directly regulate gene expression. Among all JAK family members, JAK1 signaling relates primarily to cytokines involved in inflammation.

Numerous inflammatory dermatoses are driven by soluble inflammatory mediators, which rely on JAK-STAT signaling. For example, the pathogenesis of atopic dermatitis is complex but, in part, involves increased T helper cell (Th) type 2 (ie, Th2) immunity driven by JAK-STAT signaling downstream of cytokines, such as IL-4, IL-5, and IL-13. In vitiligo, JAK-STAT also serves a central role in interferon- γ -mediated

melanocyte destruction by CD8+ T cells. In psoriasis, JAK-STAT-dependent cytokines, IL-12 and IL-23, are fundamental mediators. Interleukin-23 stimulates Th17 cells to produce IL-17, another important pathogenic molecule in psoriasis. The presence of Th17 cells in HS lesional tissue suggests that although IL-17 does not rely on JAK-STAT signaling, blockade of upstream IL-23 using JAK inhibitors may indirectly result in a decrease in Th17 cell presence and IL-17 expression.

Recent literature suggests that the main cytokines involved in HS pathogenesis are IL-1 β , IL-17, IL-23, IL-10, and, to a lesser extent, TNF- α . The expression and/or activity of these cytokines is profoundly regulated by the intracellular level through JAK-STAT signaling, and is primarily mediated by JAK1. Therefore, it can be reasonably expected that interference with the transduction of intracellular signals generated by these cytokines will modify/decrease the level of inflammation seen in HS and thus moderate or control the disease activity.

2.3 Study Rationale

JAK kinases bind to cytokine-specific receptors and, therefore, influence various aspects of the immune response. JAK1 is associated with the receptors for IFN, IL-6, and IL-10. JAK2 is mainly involved in the reaction with hematopoietic receptors as well as those for IL-12 and IL-23. JAK2 are connected with the receptors for IFN, IL-12, and IL-23. There are no published studies documenting JAK-STAT expression in HS; however, other work has shown the important role of all four kinases in other inflammatory skin conditions, such as alopecia areata, psoriasis, and vitiligo. Importantly, IL-6 and Interferon-gamma have been shown to be elevated in HS. To date in dermatology, psoriasis has been the most studied indication for JAK inhibitors including tofacitinib, baricitinib, and ruxolitinib. Incyte has completed 4 clinical studies with JAK1 and JAK2 inhibitors for the treatment of psoriasis. Topical ruxolitinib has been associated with clinical improvement and benefit in patients with chronic plaque psoriasis. Given the fact that HS shares a similar inflammatory cytokine profile as that seen in psoriasis, inhibition of JAK-STAT signaling represents a promising therapeutic strategy for the treatment of HS.

3.0 Inclusion and Exclusion Criteria

3.1 Inclusion Criteria

1. Male or female subjects age 12 years or older
 - This inclusion criteria has been updated due to the approval of the study medication for use in this age group (12 years and older) in other indications. Additionally, Humira, an approved biologic medication for HS, is also used in this population, highlighting the need for topical breakthrough treatments for those affected by HS at younger ages. Due to the open-label nature of this medication and the anticipated benefits for any children participating, the greater than minimal risk of this study design is justified.
2. Hidradenitis suppurativa, and should be Hurley Stage I or II, defined as papules, nodules, and/or abscess formation, single or multiple, with or without sinus tracts;
3. Subjects must have a diagnosis of HS for at least 3 months (90 days) prior to Baseline;
4. Active HS lesions must be present in at least one distinct anatomic area;

5. Subject must have at least 3 total inflammatory lesions at the Baseline visit;
6. Subjects who had surgery in the treatment area, should be at least 3 months status post the procedure (this applies to deroofting/marsupialization or excision, not incision & drainage)
7. Subject has a negative TB screening assessment (including a PPD test and/or T-Spot) OR for patients with treated latent TB or negative chest x-ray (CXR posterior-anterior [PA] and lateral view within prior 90 days) at Screening with documentation of treated latent tuberculosis (90 days of treatment).
8. Medications can be continued if they have been at a stable dose for the requisite duration and the dose is not increased during the study period:
 - Biologic medication (such as TNF α , IL-12/23 or IL-17 inhibitors): Up to 30% of enrolled participants will be allowed to remain on a concurrent biologic at stable dosage if treated with a stable dose and frequency for 6 months or longer;
 - Oral antibiotic must be a stable dose and frequency for 28 days or longer;
 - Hormone-based therapy (birth control pills or spironolactone) must be a stable dose and frequency for 4 months or longer;
 - Oral retinoids must be on a stable dose and frequency for 90 days or longer;
 - Other topical therapy must be discontinued 14 days prior to the Baseline visit.
 - Childbearing potential: In addition, you must be willing to use a method of contraception during the study period and for 4 weeks after the last dose of study drug. (Note: Periodic abstinence [e.g., calendar, ovulation, symptothermal, post-ovulation methods] and withdrawal are not acceptable as abstinence.)

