3.2 Exclusion Criteria

1. Non-english speaking
2. Infection(s) unrelated to HS requiring treatment with:
 - intravenous (IV) anti-infectives (antibiotics, antivirals, antifungals) within 30 days prior to Baseline or;
 - oral anti-infectives (antibiotics, antivirals, antifungals) within 14 days prior to Baseline, except as required as part of an anti-TB regimen;
3. Subject previously treated with a biologic medication but stopped due to lack of effect/sufficient effect as deemed by the investigator.
4. Any other active skin disease or condition (e.g., bacterial, fungal or viral infection) that may interfere with assessment of HS;
5. Pregnant (or considering becoming pregnant) or lactating females
Note: Nonchildbearing potential is defined as surgically sterile with a hysterectomy and/or bilateral oophorectomy OR postmenopausal (defined as amenorrhea at least 12 months before screening, confirmed by FSH levels at screening).
6. Clinically significant abnormal screening laboratory results as evaluated by the Investigator.
7. Subject does not have reliable internet access for weekly electronic surveys;
8. Subject is considered by the Study Investigator, for any reason, to be an unsuitable candidate for the study.

9. Excluded/prohibited concomitant medication and procedures include: JAK inhibitors (systemic or topical (eg, ruxolitinib, tofacitinib, baricitinib, filgotinib, lestaurtinib, and pacritinib)) within 4 weeks of Screening ; surgical, laser, or IPL intervention in area with HS lesion within 3 months of Screening, except for rescue lesional treatment; systemic corticosteroid within 4 weeks; use of topical creams, ointments, gels, and liquids except the study therapy.
10. Prolonged QT interval corrected for heart rate using Fridericia's formula (QTcF), defined as ≥ 450 msec.

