7.2 Study Procedures**7.2.1 Screening visit**

Informed consent	Laboratory screening obtained* 
 • Hepatitis B and Hepatitis C surface and core antibodies • Interferon-releasing assay for tuberculosis (or chest x-ray for those with a history of positive PPD) • Complete blood count (CBC) with differential • Hepatic panel (AST, ALT, Alk phos) • Fasting lipid panel (total, high-density, and low density cholesterol and triglycerides) • Pregnancy testing for women of child bearing potential (WOCBP)**
Inclusion/exclusion criteria reviewed	
Complete physical exam	
Clinician assessments (Lesion count, Hurley stage, HASI)	
Clinical photography of all lesions (do not include face)- kept in research files	
ECG	
Alcohol intake and recreational drug use	
Begin weekly surveys (more details below)	

*All blood will be obtained at Penn State Health outpatient laboratory.

**If subjects are postmenopausal, (defined as amenorrhea at least 12 months before screening) this will be confirmed by FSH levels drawn at the clinical site (approx. 2 teaspoons of blood)

Begin weekly surveys – These will be completed by the participants weekly through the end of Week 16 through REDCap. The weekly instruments will include patient-reported measures: NRS pain with 24-hour recall, NRS pain with 7-day recall, Hidradenitis suppurativa Quality of Life instrument (HiSQOL); medication use (assessing use of rescue medications or other potentially modifying medications or interventions).

7.2.2 Week 0, Baseline visit (28 ±5 days)- Can be combined with Screening Visit

Subjects will have a combined Screening/Baseline visit if all Inclusion/Exclusion criteria is met at the Screening visit.

Complete physical exam	Patient reported measures- collected electronically
------------------------	---

Clinician reported measures collected	WOCBP only- urine sample for pregnancy
Clinical photography	Dispense and start treatment with topical ruxolitinib 1.5% cream. Study coordinator will provide instructions for twice daily application.
Target lesion evaluated	Tissue sample collected (details below)

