Risk of systemic infections	Longer-term oral treatment with ruxolitinib can cause immunosuppression, allowing secondary infections.	Participants will be tested at the study entry for latent TB infection, chronic hepatitis,, and monitored for any signs and symptoms of infection throughout the study (eg, clinical laboratory tests, vital signs, and AE monitoring). In the event of an infection necessitating such steps, study medication can be withheld or stopped and appropriate anti-infective therapy instituted.
Headaches	Mild to moderate headaches were observed in a proportion of healthy volunteers exposed to ruxolitinib.	Possible headaches will be captured by routine AE monitoring. Analgesics may be used to relieve headache, if appropriate.

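### Inclusion criterion 7, the screening list in Section 7.2.1 and the risk table in Section 10.0 do not give one TB entry rule, so the same person can be judged differently

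*Combined protocol and SAP*

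**What the plan says.** Three places in the combined protocol and SAP deal with TB at entry.

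- **Section 3.1, inclusion criterion 7**, offers two routes. The first is a negative test: "Subject has a negative TB screening assessment (including a PPD test and/or T-Spot". The second begins "OR for patients with treated latent TB or negative chest x-ray", gives a 90-day window for the x-ray, and ends "at Screening with documentation of treated latent tuberculosis (90 days of treatment".
- **Section 7.2.1, Screening visit**, lists "Interferon-releasing assay for tuberculosis (or chest x-ray for those with a history of positive PPD" among the laboratory procedures. The same table separately lists "Inclusion/exclusion criteria reviewed".
- **Section 10.0, Risks**, in the row on systemic infections, gives as mitigation: "Participants will be tested at the study entry for latent TB infection". It names no exception.

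Section 3.2, exclusion 2, is loosely related. It exempts oral anti-infectives taken for TB from the 14-day exclusion ("except as required as part of an anti-TB regimen"). It does not say how such treatment counts towards criterion 7.

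**The concern.** The chest x-ray route is open to different people in the two operative sections. In criterion 7 it is tied to documented treated latent TB. In Section 7.2.1 it is triggered by a past positive PPD, whatever the treatment history. These groups need not coincide: a person can have a past positive PPD without documented treatment, and the text does not make a positive PPD a condition of having been treated.

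Criterion 7 is also ungrammatical at the point that matters. Its second 'or' presents treatment and x-ray as alternatives, while the closing phrase joins the x-ray to proof of treatment.

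What is at stake is consistent eligibility and a stated safeguard. Two coordinators who follow the text in good faith could decide differently about the same person. Screening and Baseline may be combined, and study drug is dispensed at Baseline, so the decision may have to be made at one visit. The protocol itself offers latent TB testing at entry as mitigation for infection risk, so the procedure should visibly deliver it.

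**Working it through.** No arithmetic applies. The plan states no figure on this point, and none of its sample-size or analysis inputs enters. The check sets the passages side by side and takes test cases through them.

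**Step 1. Possible readings of the second route in criterion 7.**

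- Reading 1: treated latent TB is enough, or else a negative x-ray together with documented treatment. This takes the second 'or' literally and keeps the closing phrase on the x-ray clause that it directly follows. Both limbs require treatment.
- Reading 2: treatment and a negative x-ray are both required. This takes the second 'or' as a slip.
- Reading 3: a negative x-ray is a route of its own. This detaches the documentation phrase from the clause next to it. It is the least natural reading, but the broken sentence does not rule it out.

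**Step 2. What Section 7.2.1 requires.** It requires the interferon assay, or an x-ray if there is a history of positive PPD. It mentions neither treatment, nor its documentation, nor the 90-day x-ray window. PPD, which criterion 7 accepts as a test, is not on the list.

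**Step 3. Two cases.** In both, no assay or PPD is done at screening.

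| Person | TB item in 7.2.1 | Criterion 7, reading 1 | Reading 2 | Reading 3 |
|---|---|---|---|---|
| Past positive PPD, clear x-ray within 90 days, no documented treatment | completed | not met | not met | met |
| Past positive PPD, documented 90-day treatment, no x-ray | not completed | met | not met | met |

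The first person completes the TB item in Section 7.2.1 under every reading but meets criterion 7 only under reading 3. Under readings 1 and 2 this person could still enter through a negative test, but Section 7.2.1 does not call for that test once the x-ray is done. The second person shows the milder ambiguity: whether treatment needs an x-ray beside it.

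**Step 4. Comparison with Section 10.0.** The risk table says that participants are tested at entry for latent TB. Section 7.2.1 gives the x-ray as a substitute for the assay, and no passage says that the x-ray counts as the latent TB test. On its face, then, the procedure does not assure the stated test for those who have only the x-ray.

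**Step 5. Size.** Section 8.1 anticipates screening and enrolling about 24 people. The documents do not say how many would have a past positive PPD, so no count can be derived. In a study of this size it is likely to be small; one such person would be 1/24, or about 4%, of the anticipated number.

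**The case against.** The strongest answer is that Section 7.2.1 is a list of procedures and admits nobody. The same table calls for a review of the entry criteria, and the combined Screening/Baseline visit is allowed only when all of them are met. Criterion 7 therefore governs, and its more natural reading keeps documented treatment attached to the x-ray. All of this stands, and it limits the point. It does not remove it, because the review applies the very sentence that cannot be read in one way.

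A reader might go further and infer any of the following, none of which the documents support:

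- *That people with a past positive PPD get only an x-ray.* Section 7.2.1 says 'or'. The assay is not required for them, but it is not barred.
- *That the plan admits untreated latent TB and also shuts out people who should qualify.* The first needs reading 3. The second needs reading 1 or 2, and also a site that does no further test. The two come from opposite readings and cannot be added together. Someone who meets neither route of criterion 7 is not eligible under the text in any case.
- *That the gap falls on participants taking a TNF inhibitor or other biologic.* The 30% in Section 3.1 is a cap on all enrolment and says nothing about who has a past positive PPD.
- *That the infection safeguard fails as a whole.* The Section 10.0 row concerns longer-term oral treatment. It also names infection monitoring and the withholding or stopping of study medication, and the same section describes low systemic exposure from the cream.

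**Conclusion.** The point holds as an internal inconsistency in an operative eligibility and safety-screening rule. Criterion 7 and Section 7.2.1 define the x-ray route for different groups, criterion 7 can be read in at least two tenable ways and a third less plausible one, and Section 7.2.1 does not assure the entry test that Section 10.0 states. It is more than a slip in background text, because staff use these passages to decide who enters.

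The effect is small. Few participants are likely to be concerned, though the documents give no frequency, and neither the sample size nor the primary analysis changes. The conclusion rests on the wording alone. The remark about Section 10.0 also takes the x-ray as not being the latent TB test meant there; the documents do not say either way. Preferring the restrictive reading of criterion 7 is a judgement on its grammar, not a view on which TB rule is clinically right.

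**What to change.** Reconcile Section 3.1 criterion 7, Section 7.2.1 and the infection row of Section 10.0, so that all three give one answer for a person with a past positive PPD, a clear x-ray and no documented treatment. Within that:

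- Rewrite the second route of criterion 7 so that it states plainly how treatment documentation and x-ray combine.
- Make the condition for the x-ray in Section 7.2.1 the same as in criterion 7, including what must be documented and the time window.
- Word Section 10.0 so that it describes what the agreed procedure delivers.

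The clinical content of the rule is for the sponsor's clinical lead to decide. The change itself is a wording amendment to existing sections and needs no change to the design or analysis. Whether it alters any screening procedure depends on the rule chosen.
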